### Brief Description

This study will be the pilot/feasibility phase of a future clinical trial. The proposed feasibility and pilot study aims to bridge the barriers to diagnosis by providing easy-to-access assessment for free, through a mobile unit that travels to rural locations and telehealth assessments. The diagnostic evaluation will confirm or rule out a diagnosis of ASD, followed by purposeful ASD psychoeducation for parents whose children are diagnosed.

Parents of children who meet criteria for a diagnosis of autism spectrum disorder (ASD) or are suspected to have ASD will be randomized into one of three groups (i.e., in-person psychoeducation, telehealth psychoeducation, or "psychoeducation as usual" with paper psychoeducation materials). Parents will complete outcome measures related to their satisfaction, empowerment, and autism spectrum disorder knowledge. Changes in empowerment and ASD knowledge from pre- to post-psychoeducation will be measured using t-tests. The investigators will also track if participants sought and/or received additional ASD-related services throughout the study, up to 6-months post-psychoeducation. Results from this study will help to guide a future, fully powered efficacy trial with a larger sample.

Added April 2020:

In light of the Virginia governor's stay-at-home order in response to the COVID-19 outbreak, which reached pandemic status approximately halfway through data collection, all in-person research and clinical services have been paused at Virginia Tech as of March 13, 2020. To continue to provide services to families in this time, in line with Executive Order 53 from the VA Governor to ensure that the stay-at-home orders do not limit the provision of health care or medical services, this study will begin exploring the feasibility of conducting tele-assessment, a comprehensive assessment battery via a secure video platform and phone.

As such, the protocol is altered to be in line with the university's request to move to remote conduct of research where possible. For the remaining half of participants, the investigators will replace the mobile assessment battery with a tele-assessment battery, delivered via secure online video platform ZoomHIPAA and/or by phone (totaling up to 7 hours of assessment). As such, the protocol is revised to include tele-assessments (no in-person assessments) and randomly assigning eligible participants to either the telehealth or paper materials psychoeducation groups. All outcome measures will remain the same, but will be collected online or by telephone. The investigators and participants may return to in-person assessments if and when it is possible, but reserve the right to continue tele-assessment even once stay-at-home orders are lifted.

The primary aim remains the feasibility and satisfaction with psychoeducation, as this is a pilot feasibility study. The secondary aim will be significantly underpowered to analyze the differences between psychoeducation conditions (i.e., in-person vs. telehealth psychoeducation), therefore in person and telehealth conditions will be combined into one psychoeducation (PE) group with clinician-led sessions. The mean differences between the PE group and the

psychoeducation as usual (i.e., paper materials) formats will be preliminarily explored in terms of changes in outcome measures (i.e., FES and ASK-Q).

## Protocol

**Participants:** Participants will be recruited primarily from locales served by the Mount Rogers Community Services Board (MRCSB), including Smyth, Wythe, Bland, Carroll, and Grayson counties, and Galax City, in rural southwest Virginia, but we will also accept families from other local communities who contacted us to participate. We aim for 21 children between 2-15 years of age and one primary caregivers. Following a diagnostic feedback session, caregivers of children who receive an ASD diagnosis will be randomized to either attend psychoeducation sessions or receive comparable psychoeducation materials about ASD, with the goal of assessing feasibility and satisfaction of psychoeducation and of improving caregiver ASD knowledge and empowerment to seek and provide care for their child. Initially, families were going to be randomized to the following three psychoeducation conditions. Following the stay-at-home orders during the COVID-19 pandemic, however, we had to combine the first two conditions into one psychoeducation (PE) condition with clinician-led sessions. The psychoeducation as usual (PAU) condition, remained the same.

*1) In-person Psychoeducation Sessions:* Caregivers in this group attended two 90-minute, in-person psychoeducation sessions on our mobile autism clinic (MAC), in or near their hometown. During these sessions, a clinician presented a series of psychoeducation topics supplemented with PowerPoint slides. The first session covered signs/symptoms of ASD, risk factors associated with developing ASD (e.g., heritability, neurobiology, social motivation), and navigating the service systems (e.g., Individualized Education Program (IEP) process, insurance, and Medicaid waivers), while the second psychoeducation session covered evidence-based best practices and a basic introduction to behavior management principles. This delivery method allowed caregivers an opportunity to ask questions and receive immediate, live, and detailed answers from an expert clinician, to focus on specific examples relevant to their child.

*2) Telehealth Psychoeducation Sessions:* Caregivers in this group also attended two 90-minute sessions, but remotely via a video chat platform, rather than in-person. Otherwise, it followed the same format and PowerPoint materials as the in-person group. Sessions were still facilitated by a clinician, thereby maintaining the option to ask questions, discuss personalized examples, etc. This telehealth method of delivery allowed for more flexibility in scheduling, as sessions could be conducted on days when the MAC was not in-service, but required additional consideration for families who did not have a computer and Internet access. In these cases, a family was randomized to one of the other two psychoeducation groups.

*3) Psychoeducation as usual (PAU) - Informational Materials:* Caregivers in this group received basic paper psychoeducation resources, distributed at their feedback session. It was up to each caregiver how frequently and diligently they reviewed these resources, but they were encouraged to review them over the course of the following two weeks. These materials were intended to be akin to what a family might have access to at their pediatrician or primary care office, or perhaps on a website, if they were to look for ASD information on the Internet. To be consistent across study groups, the materials produced for these caregivers were comprehensive and included the same span of content as the PowerPoint slides used in the other two groups, but without structured sessions facilitated by a clinician. Upon distribution of materials, caregivers

were encouraged to reach out via phone or email if they had any questions, but only one caregiver did so.

### Procedures

To track outcomes, caregivers completed a series of measures at five time points: (1) Time 1: intake, (2) Time 2: after feedback session, pre-psychoeducation, (3) Time 3: post-psychoeducation (i.e., after the second psychoeducation session or equivalent time after feedback for PAU group), (4) Time 4: at 6-week follow-up from the end of psychoeducation, and (5) Time 5: at 6-months follow-up from the end of psychoeducation. Times 1-4 consisted of measures of caregiver empowerment and ASD knowledge; Time 1 included measures of current services; Times 2-5 included a measure of new additional services since the prior timepoint; and Time 3 also included a measure of satisfaction with the psychoeducation services.

### Measures

#### *Primary Outcome Measures*

Primary outcomes include the assessment of feasibility and satisfaction.

*Feasibility* of the study will be assessed by tracking the number of parents who completed the psychoeducation sessions and the attrition from Time 2 to Time 3.

*Caregiver satisfaction* with our psychoeducation services will be collected at Time 3 (the end of the final psychoeducation session or after two weeks of materials for the PAU group). This survey includes 32 questions on a 5-point Likert Scale from 0 (Completely Disagree) to 4 (Completely Agree). This measure surveys areas of convenience, process, quality, interpersonal sensitivity, satisfaction with psychoeducation, and general satisfaction. Because scales have varying numbers of items, each subscale is calculated by adding the item scores and dividing by the number of items in that scale, for a mean score ranging from 0 to 4. For the current study, we will sum 5 items related specifically to the psychoeducation services, for a possible total of 20. Higher mean scores indicate greater satisfaction.

#### *Secondary Outcome Measures*

*Family Empowerment Scale* (FES; Koren et al., 1992) measures levels of perceived efficacy in areas such as community involvement and navigating services for the child and family. The FES is a 34-item questionnaire, providing a 5-point Likert scale for each item. The FES provides raw sums of the items within three domains of empowerment: Family (max = 60), Service System (max = 60), and Community/Political (max = 50). A higher raw score indicates greater empowerment in a given area. These factors are conceptually meaningful, congruence between them is high, and internal consistency is strong (.78-.89; Singh et al., 1995). In the current study, a sum total of all scales will be obtained, and a change score will be calculated between pre- and post-intervention. Positive scores indicate an increase in empowerment.

Caregivers also reported on their ASD knowledge and beliefs on the *Autism Stigma and Knowledge Questionnaire* (ASK-Q; Harrison et al., 2017). The ASK-Q consists of 49 True/False statements, which comprise four subscales of ASD knowledge: diagnosis, etiology, treatment,

and stigma, which results in a raw total score. The ASK-Q demonstrates strong internal consistency (.88). The knowledge subscales – diagnosis, etiology, and treatment – as well as the total score were used in this study. The items on this measure demonstrate strong face and construct validity, as well as cross-cultural utility. It also demonstrates strong discrimination between those who do and do not have adequate knowledge about ASD. In the current study, a sum total of all scales will be obtained, and a change score will be calculated between pre- and post-intervention. Positive scores indicate an increase in knowledge.

Parents will complete a *New Services Survey* to assess additional services they have received since the prior timepoint. In the current study, we will calculate the number of families in each condition (PE and PAU) that added any new service across all timepoints for the duration of the study up to 6 months post-psychoeducation.

#### Statistical Analysis Plan

For Aim 1, the feasibility aim of this study, primary analyses will include tracking completion and attrition with the psychoeducation services across both groups: PE and PAU. These analyses will be descriptive only. Additionally, we will compare each group on satisfaction with the psychoeducation services. Independent t-tests will compare total satisfaction scores between the PE and PAU groups.

For the second aim, we will assess the differential efficacy across the PE and PAU conditions on the measures of caregiver empowerment and ASD knowledge, as well as new services received. First, we will calculate the change score (Time 3 minus Time 2) for the FES total score and the ASK-Q total score to determine the change in empowerment and knowledge from pre- to post-psychoeducation. Independent t-tests will compare the PE and PAU conditions on FES change score and on ASK-Q change score. To assess new services received, we will calculate the percent of families in each condition (PE and PAU) that indicated receiving a new service at any timepoint over the course of the study up to the 6-month follow-up. This analysis will be descriptive only.

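### Does Aim 1 need a planned summary of completion, attrition and satisfaction for in-person and telehealth sessions separately?

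*Combined protocol and SAP*

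**What the plan says.** For Aim 1, the Statistical Analysis Plan states that "primary analyses will include tracking completion and attrition with the psychoeducation services across both groups: PE and PAU", and it makes these summaries descriptive. For satisfaction, "Independent t-tests will compare total satisfaction scores between the PE and PAU groups".

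PE is defined in two places:

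- The April 2020 addition to the Brief Description says "The secondary aim will be significantly underpowered to analyze the differences between psychoeducation conditions", and continues "therefore in person and telehealth conditions will be combined into one psychoeducation (PE) group with clinician-led sessions".
- The Protocol section, under Participants, gives a different reason: "Following the stay-at-home orders during the COVID-19 pandemic, however, we had to combine the first two conditions". That sentence is not tied to any one aim.

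Delivery mode was also shaped by events and access. The Brief Description reports that "all in-person research and clinical services have been paused at Virginia Tech as of March 13, 2020" and moves to "randomly assigning eligible participants to either the telehealth or paper materials psychoeducation groups". For families without a computer and Internet access, the telehealth paragraph of the Protocol section says "In these cases, a family was randomized to one of the other two psychoeducation groups".

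No section attaches a summary or a test to in-person versus telehealth.

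**The concern.** Feasibility and satisfaction are the primary aim, and the Brief Description says the results are meant to guide a later, larger trial. The two modes make different practical demands: one needs the mobile clinic near the family's home, the other needs equipment and a connection. A single PE figure cannot show how feasible either mode was.

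The power argument in the Brief Description is made for the secondary aim. A count of completers needs no power, so that argument does not explain why Aim 1 is also reported only for the merged group.

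The mix of modes within PE was not fully fixed by design either. It depends on when in-person work stopped and on how many families lacked Internet access. If one mode had kept its families and the other had lost them, the pooled figure could hide this, and the planners of the next trial would not see it.

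**Working it through.** **1. Text.** The plan gives no allocation ratio, arm size or target completion rate, so there is no figure of its own to reproduce. The sections do confirm that no summary by mode is planned. Three further points decide what follows from that:

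- The merger in the Protocol section is general. It replaces two conditions by one clinician-led condition, whichever aim is being analysed.
- The telehealth paragraph says that, apart from being remote, those sessions kept the in-person format and slides and were led by a clinician. Clinician-led sessions against paper materials is therefore a coherent contrast.
- The Aim 1 sentence says what the primary analyses will include. It does not say that nothing else may be reported.

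**2. How many families each mode would have.** Assumptions: N = 21 families randomised (21 is the plan's target for children); a fraction f enters before the revision; a fraction u has no Internet access. Allocation is 1:1:1 before the revision and 1:1 after it. Families without access are split 1:1 between in-person and PAU before the revision and go to PAU after it.

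- In-person = N·f·[(1−u)/3 + u/2]
- Telehealth = N·f·(1−u)/3 + N·(1−f)·(1−u)/2

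| f | u | In-person | Telehealth | In-person share of PE |
|---|---|---|---|---|
| 0.5 | 0 | 3.50 | 8.75 | 28.6% |
| 0.5 | 0.2 | 3.85 | 7.00 | 35.5% |
| 0.4 | 0 | 2.80 | 9.10 | 23.5% |
| 0.6 | 0.2 | 4.62 | 6.72 | 40.7% |

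The last two rows give the lowest and highest in-person share for f from 0.4 to 0.6 and u from 0 to 0.2. If only 15 are randomised, the same two rows give 2.00 and 6.50, and 3.30 and 4.80.

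**3. What the mix could do to the pooled figure.** Suppose, purely as a hypothesis, that completion is 50% in-person and 100% by telehealth.

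- Lowest share: 1 − 0.5 × 0.235 = 88.2%; expected non-completers 0.5 × 2.80 = 1.40 of 11.90.
- Highest share: 1 − 0.5 × 0.407 = 79.6%; expected non-completers 0.5 × 4.62 = 2.31 of 11.34.
- Difference in non-completers: 2.31 − 1.40 = 0.91 of one family.

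The swing of about 8 percentage points needs a 50-point gap between modes and opposite corners of the assumed grid. It still amounts to less than one family.

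**4. What a split could show.** Take a hypothetical 4 in-person and 7 telehealth families with 9 of 11 completing (82%, exact 95% CI 48% to 98%). Two possible splits, with Clopper-Pearson intervals and two-sided Fisher tests:

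| In-person | Telehealth | Fisher p |
|---|---|---|
| 2/4 (7% to 93%) | 7/7 (59% to 100%) | 6/55 = 0.109 |
| 4/4 (40% to 100%) | 5/7 (29% to 96%) | 27/55 = 0.491 |

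Pooling can conceal which pattern occurred, but neither pattern supports a conclusion about modes. Mode is also confounded: after the revision there is no in-person arm, assessment moves to video and telephone, and families without Internet access do not receive telehealth.

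**The case for a change.** The best case for the concern is that a feasibility study exists to inform the next design, and raw counts by mode cost almost nothing. They need no new data, provided that assigned mode is in the randomisation record. The secondary-aim power argument does not reach descriptive counts, and fixing the table in advance would keep the choice to report by mode from depending on the results.

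Some of this stands. No summary by mode is planned, counts need no power, and a sensible team may well report them.

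It does not make the plan deficient. The power sentence is not the only ground for merging, because the Protocol section gives a general one. That the later trial will use both modes, or a different mix of them, is a supposition: the Brief Description says only that the results will help to guide it. A formal table with intervals such as 29% to 100% for 3/3 would invite over-reading, and individual satisfaction values for a handful of families from a few named rural localities could raise a disclosure problem.

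How families assigned to in-person sessions but unfinished at the March 2020 pause were handled is a separate question. It does not bear on whether Aim 1 may be reported by PE and PAU.

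**Conclusion.** The concern does not hold. Reporting Aim 1 by PE and PAU follows the stated merger of the two clinician-led modes and matches the question that the revised study asks. The missing split makes no planned test or estimate invalid, and nothing prevents the team from listing counts by mode in the report.

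Such a listing would rest on about 3 to 5 in-person and 7 to 9 telehealth families (about 2 to 3 and 5 to 7 if 15 are randomised) and could not support a statement about either mode against the other. Those sizes depend on the assumed allocation, timing and Internet access, and on no in-person sessions being assigned after the revision. The Brief Description allows in-person assessments to resume but does not say whether in-person psychoeducation would, so the in-person count could be higher. The textual reasons do not depend on these figures.

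### Low priority: Aim 2 compares PE and PAU on raw change without using the Time 2 score as a covariate; a baseline-adjusted estimate alongside it is cheap, but the precision gain is conditional

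*Combined protocol and SAP*

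**What the plan says.** The Statistical Analysis Plan defines the Aim 2 outcome as raw change: "First, we will calculate the change score (Time 3 minus Time 2) for the FES total score and the ASK-Q total score". The comparison follows directly: "Independent t-tests will compare the PE and PAU conditions on FES change score and on ASK-Q change score". No covariate is named, and the section mentions tests but no confidence interval.

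Procedures shows that more is collected than this analysis uses: "Times 1-4 consisted of measures of caregiver empowerment and ASD knowledge", where Time 4 is the 6-week follow-up. No section says how the Time 4 FES and ASK-Q scores will be analysed. The only stated analysis beyond Time 3 is the descriptive percentage of families with new services.

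On sample size, Protocol (Participants) says "We aim for 21 children between 2-15 years of age". It also says "Following a diagnostic feedback session, caregivers of children who receive an ASD diagnosis will be randomized to either attend psychoeducation sessions" or to receive materials, so 21 is a recruitment target and the number randomised may be smaller. The text added to Brief Description in April 2020 keeps feasibility and satisfaction as the primary aim and treats the PE-PAU comparison as preliminary.

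**The concern.** A t-test on Time 3 minus Time 2 is the same as a regression of the Time 3 score on condition with the Time 2 coefficient forced to 1. The true coefficient is rho x (SD post / SD pre). If that is well below 1, subtracting the whole baseline adds noise that an estimated coefficient would remove.

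Brief Description says the results will guide a fully powered trial. The useful product of Aim 2 is therefore an estimated difference with its uncertainty. Avoidable width in that interval is the loss, and it concerns a secondary aim only.

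**Working it through.** **Inputs from the documents.** Target of 21 children (Protocol, Participants); outcome and test (Statistical Analysis Plan). The documents give no power calculation, effect size, SD or correlation, so there is no figure of theirs to reproduce.

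**Assumptions.** Two-sided 95% intervals; the same SDs and slope in both conditions; rho 0.5, 0.7, 0.8; SD ratio k = SD post / SD pre of 0.8, 1.0, 1.1, 1.25; analysed N of 21, 15 or 12.

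**Formulas**, with SD pre = 1:

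- Var(change) = 1 + k² - 2·rho·k
- ANCOVA residual variance = k²(1 - rho²)
- Difference = (1 - rho·k)², which is zero only at slope rho·k = 1
- Cost of estimating the slope: factor 1 + 1/(N - 4) on the variance for chance baseline imbalance, and N - 3 rather than N - 2 degrees of freedom
- CI width ratio, ANCOVA to change = sqrt[k²(1 - rho²)(1 + 1/(N - 4)) / (1 + k² - 2·rho·k)] x t(0.975, N - 3) / t(0.975, N - 2)

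**Worked case**, N=21, rho 0.7, k=1: variances 0.60 and 0.51. Ratio = sqrt(0.51 x 1.0588 / 0.60) x 2.1009/2.0930 = 0.952, or 4.8% narrower. At an assumed 12:9 split, sqrt(1/12 + 1/9) = 0.441. The half-width goes from 2.093 x sqrt(0.60) x 0.441 = 0.715 to 2.101 x sqrt(0.51 x 1.0588) x 0.441 = 0.681, in Time 2 SD units.

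**Change in CI width with ANCOVA (%), at rho 0.5 / 0.7 / 0.8**

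| SD ratio | N=21 | N=15 | N=12 |
|---|---|---|---|
| 0.8 | -21.9 / -18.2 / -17.4 | -20.4 / -16.5 / -15.7 | -18.6 / -14.7 / -13.9 |
| 1.0 | -10.6 / -4.8 / -2.0 | -8.8 / -2.9 / -0.1 | -6.7 / -0.7 / +2.2 |
| 1.1 | -6.6 / -0.9 / +1.6 | -4.8 / +1.1 / +3.6 | -2.6 / +3.3 / +5.9 |
| 1.25 | -2.4 / +2.3 / +3.3 | -0.5 / +4.3 / +5.3 | +1.8 / +6.6 / +7.7 |

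**Break-even.** With equal SDs the gain ends at rho 0.875 (N=21), 0.80 (N=15) and 0.725 (N=12).

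**Worst case**, slope exactly 1: sqrt(1 + 1/17) x 2.1009/2.0930 = 1.033 at N=21. The same formula gives 1.053 at N=15 and 1.077 at N=12.

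**Simulation check.** With 40,000 replicates per setting at splits 14:7, 11:10 and 10:5, the CI width ratios agreed with the formula to about 0.005, and both methods kept about 95% coverage. At 12:9 with equal SDs and a true difference of 0.5 SD, simulated power rises from 19% to 23%, 28% to 31% and 40% to 41% at the three values of rho.

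**The case against.** The strongest reply is that this is mostly preference. The plan defines the outcome as change consistently, the documents already call the comparison preliminary, and a half-width moving from 0.71 to 0.68 SD would alter no pilot conclusion. That stands, and it is why the point is low priority.

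The direction of the effect on precision is also unknown. At N=12 and N=15 with SD ratio 1.1 or 1.25, ANCOVA gives the wider interval in 9 of the 12 cells above. The interval between Time 2 and Time 3 is short (about two weeks for PAU), so rho above 0.8 is possible. At rho 0.9 with equal SDs ANCOVA is 1% wider at N=21, 3% at N=15 and 5% at N=12. A reader might infer that a gain is likely or holds in most plausible settings. Without rho or SDs in the documents, that cannot be said.

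Timing matters too. Protocol already reports delivery in the past tense; of PAU caregivers invited to ask questions it says "but only one caregiver did so". Replacing the planned test after outcomes have been seen would be a post hoc choice. This stands and shapes the fix.

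Two stronger readings should be resisted.

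- A reader might infer that the unadjusted t-test is biased or invalid. Randomisation protects a change-score comparison as it does an adjusted one. The mid-study move from three conditions to two, and the rule for families without a computer and Internet, may make the PE:PAU allocation probability vary by period and access. That is a separate question, which adjusting for Time 2 does not resolve.
- A reader might infer that the PAU baseline is contaminated. Procedures has "Time 2: after feedback session, pre-psychoeducation", while Protocol says PAU caregivers "received basic paper psychoeducation resources, distributed at their feedback session". The order of questionnaire, allocation and hand-out is simply not stated; nothing shows that materials came first.

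**Conclusion.** The point holds as a cheap, low-priority improvement. Aim 2 leaves the Time 2 total unused as a covariate. The planned test is not invalid on that account, and the aim is secondary and preliminary.

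The benefit depends on rho, the SD ratio and the analysed N, all of which are assumptions here. At N=21 it runs from intervals about 22% narrower to about 3% wider over the grid shown. It disappears as the slope approaches 1, and sooner in smaller samples. The loss is bounded whatever rho and the SD ratio: at most 3.3% at N=21, 5.3% at N=15 and 7.7% at N=12. ANCOVA does not cure the low power.

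The missing Time 4 analysis and the unstated order around Time 2 are gaps in detail and do not add to the severity.

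**What to change.** For the FES total and the ASK-Q total, report the PE-PAU adjusted mean difference with 95% CI from an ANCOVA of the Time 3 total on condition and the Time 2 total, alongside the planned change-score t-test.

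Date the change and state whether any outcome data had been seen. If none had, ANCOVA may be the main estimate. Otherwise keep the t-test as planned and label ANCOVA supportive.

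The same adjusted contrast at Time 4 may be reported as an exploratory 6-week estimate with its CI. One sentence should confirm whether Time 2 is completed before allocation is disclosed and PAU materials are handed out.

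The cost is SAP wording and one degree of freedom per model. Two methods on two outcomes make four Aim 2 analyses at Time 3, besides the Aim 1 satisfaction t-test, so the report should say which is the main one for each outcome.

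### The ever/never summary of new services drops the timing of the four surveys and counts services gained before psychoeducation began

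*Combined protocol and SAP*

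**What the plan says.** The Procedures section sets five time points. At intake, "Time 1 included measures of current services". After that, "Times 2-5 included a measure of new additional services since the prior timepoint". The second time point is defined as "Time 2: after feedback session, pre-psychoeducation". Empowerment and knowledge are measured at Times 1 to 4 only, so new services are the one outcome collected at Time 5, 6 months after psychoeducation ends.

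Under Secondary Outcome Measures, the New Services Survey is used "to assess additional services they have received since the prior timepoint". The summary planned there is "the number of families in each condition (PE and PAU) that added any new service across all timepoints". The Statistical Analysis Plan restates it as "the percent of families in each condition (PE and PAU) that indicated receiving a new service at any timepoint", places it under the second aim (differential efficacy of PE and PAU), and makes the analysis descriptive.

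Neither section plans a summary by time point, a count of services, a time to first service, or any use of the Time 1 services in this analysis.

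**The concern.** An ever/never summary treats a family that gained a service before the intervention, one that gained it two weeks later and one that gained it at 6 months as the same. After the first service, nothing later changes the family's value.

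Two consequences matter for a comparison of conditions. First, a family that reports a service at Time 2 is fixed at yes before psychoeducation starts and can no longer contribute to a difference. Second, if most families gain something within 6 months in both conditions, the percentages sit near 100% and differences in how much or how soon are hidden.

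What is at stake is what the pilot hands on. The Brief Description says its results will guide a fully powered trial. A single cumulative percentage does not tell that trial when uptake happens, how much of it precedes the intervention, or what the mean and spread of a service count would be.

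**Working it through.** The plan states no rate, sample size or power figure for new services, so there is nothing of its own to reproduce. Step 1 is read from the documents. Steps 2 to 4 are illustrations on assumed rates.

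**1. What each survey covers** (Procedures; Secondary Outcome Measures)

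| Survey | Look-back | Relation to psychoeducation |
|---|---|---|
| Time 2 | intake to after feedback | before |
| Time 3 | Time 2 to end of psychoeducation | during |
| Time 4 | Time 3 to 6 weeks after | after |
| Time 5 | Time 4 to 6 months after | after |

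The Protocol section places randomization after the feedback session: "caregivers of children who receive an ASD diagnosis will be randomized". The Time 2 look-back therefore lies before the intervention in both conditions, yet the wording of the summary includes it.

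**2. Dilution from Time 2.** Let q be the share of families with a new service by Time 2, the same in both conditions and independent of later uptake (assumed). Let p be the share with a new service at Times 3 to 5. The planned percentage is 1 − (1 − q)(1 − p), so the difference is (1 − q)(p_PE − p_PAU). With assumed p of 50% (PAU) and 80% (PE):

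| q | PAU | PE | Difference (points) |
|---|---|---|---|
| 0 | 50% | 80% | 30 |
| 0.1 | 55% | 82% | 27 |
| 0.2 | 60% | 84% | 24 |
| 0.5 | 75% | 90% | 15 |

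**3. Is there a ceiling?** If a share p of families reports a new service at each survey, independently, the share with at least one over k surveys is 1 − (1 − p)^k.

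| p per survey | k = 4 (Times 2–5) | k = 3 (Times 3–5) |
|---|---|---|
| 0.1 | 34% | 27% |
| 0.2 | 59% | 49% |
| 0.3 | 76% | 66% |
| 0.4 | 87% | 78% |
| 0.5 | 94% | 88% |

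The ceiling is near only when about 40–50% or more of families report something at each survey.

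**4. What is lost against a count.** With Poisson counts of mean m, the share with at least one is 1 − exp(−m). If PE truly doubles the PAU mean, the difference is exp(−m) − exp(−2m): 17, 24, 23, 12 and 5 points at m = 0.25, 0.5, 1, 2 and 3.

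For relative information, take 9 PAU and 12 PE families. This split is assumed; the plan gives none. At means of 2 versus 3:

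- Ever/never: 86.5% versus 95.0%. Signal/SE = 0.0855 / √(0.865 × 0.135/9 + 0.950 × 0.050/12) = 0.0855 / 0.130 = 0.66.
- Count: 1.0 / √(2/9 + 3/12) = 1.0 / 0.687 = 1.46.
- Squared ratio: about 0.20, so ever/never keeps about 20% of the information.

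The same formulas give about 10% kept at 3 versus 4, 49% at 1 versus 1.5, 72% at 0.5 versus 0.75 and 85% at 0.25 versus 0.375.

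If counts vary more between families (variance = mean + mean²), the share with at least one is 1 − 1/(1 + m). Means of 2 versus 3 then give 67% versus 75%, and about 29% of the information is kept. The loss remains, but the near-ceiling does not.

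**The case against.** The strongest reply is that this is a secondary endpoint in a pilot, summarised descriptively, with no test, sample size or decision resting on it. The Brief Description speaks of tracking whether families sought or received services, and a percentage answers that question. Extra rows are useful description, and leaving them out is not an error of analysis. This stands, and it sets the severity.

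Four stronger readings are tempting, and the documents do not support them.

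- *The measure saturates.* No uptake rate is given. Uptake could be high after a new diagnosis, but the families are rural and were recruited because access is difficult. At 10–20% per survey the four-survey figure is 34–59%, and at low means little is lost. A ceiling is a possibility only.
- *The surveys already record how many services, or which.* The form is not shown. Only the look-back interval is explicit, so a count may not be available.
- *A count would separate a minor service from a full programme.* It would not, because each still scores one. Counts also bring double counting and depend on every survey being returned.
- *Including Time 2 biases the comparison towards one condition.* The services precede randomization, so the expected effect is dilution, plus chance imbalance in a small sample.

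In addition, no scenario in the information comparison takes the count's signal/SE above 1.46, so neither summary would be conclusive there. The reply does not answer the inclusion of Time 2 in an efficacy comparison, which holds whether or not there is a ceiling.

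**Conclusion.** The point holds as a minor one. Three parts can be read from the documents without assumptions: four surveys become one yes/no per family, interval timing drops out of the planned analysis, and services reported before psychoeducation count towards the PE versus PAU comparison.

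The sizes are conditional. The Time 2 dilution is a factor of 1 − q, with q unknown. The loss against a count runs from slight (about 85% of the information kept at means of 0.25 versus 0.375) to severe (about 10% at 3 versus 4). It rests on assumed Poisson means, an assumed split of the 21 and a survey that records individual services. No test or sample size is affected.

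**What to change.** In Secondary Outcome Measures and the Statistical Analysis Plan:

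1. Keep the planned percentage over the whole study, but base the PE versus PAU comparison on new services reported at Times 3 to 5. Show Time 2 separately, as pre-psychoeducation uptake.
2. Report the percentage by survey interval in each condition. State the length of each interval, because they are unequal.
3. If the form records individual services, add the number of distinct new services per family over Times 3 to 5 in each condition: mean, median, range, and the difference with a 95% CI labelled exploratory. Show the Time 1 current services alongside. If the form records only yes or no, items 1 and 2 still apply.
4. Show the number of surveys completed in each condition, because an unreturned survey can look like no new service.

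The cost is a few table rows from surveys already scheduled, plus a coding rule so that one service is not counted twice across surveys. Counts are sensitive to missed surveys, which is why item 4 is needed.
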